8.8 Hepatitis or Hepatic function decline

For **Grade 2** events, monitor liver function tests more frequently until returned to baseline values (consider weekly).

- Treat with IV or oral corticosteroids

For **Grade 3-4** events, treat with intravenous corticosteroids for 24 to 48 hours.

- When symptoms improve to Grade 1 or less, a steroid taper should be started and continued over no less than 4 weeks.

8.9a Renal Failure or Nephritis

For **Grade 2** events, treat with corticosteroids.

For **Grade 3-4** events, treat with systemic corticosteroids.

- When symptoms improve to Grade 1 or less, steroid taper should be started and continued over no less than 4 weeks.

8.9b Management of Infusion Reactions: Signs and symptoms usually develop during or shortly after drug infusion and generally resolve completely within 24 hours of completion of infusion. The table below shows treatment guidelines for subjects who experience an infusion reaction associated with administration of pembrolizumab (MK-3475).

Infusion Reaction Treatment Guidelines

NCI CTCAE Grade	Treatment	Premedication at subsequent dosing
Grade 1 Mild reaction; infusion interruption not indicated; intervention not indicated	Increase monitoring of vital signs as medically indicated until the subject is deemed medically stable in the opinion of the investigator.	None
Grade 2 Requires infusion interruption but responds promptly to symptomatic treatment (e.g., antihistamines, NSAIDS, narcotics, IV fluids); prophylactic medications indicated for <=24 hrs.	
Stop Infusion and monitor symptoms.
 
Additional appropriate medical therapy may include but is not limited to:
 
 IV fluids Antihistamines NSAIDS Acetaminophen Narcotics 
Increase monitoring of vital signs as medically indicated until the subject is deemed medically stable in the opinion of the investigator.
 
If symptoms resolve within one hour of stopping drug infusion, the infusion may be restarted at 50% of the original infusion rate (e.g., from 100 mL/hr to 50 mL/hr). Otherwise dosing will be held until symptoms resolve and the subject should be premedicated for the next scheduled dose.
 
Subjects who develop Grade 2 toxicity despite adequate premedication should be permanently discontinued from further trial treatment administration.
	
Subject may be premedicated 1.5h (\pm 30 minutes) prior to infusion of pembrolizumab (MK-3475) with:
 
Diphenhydramine 50 mg P.O. (or equivalent dose of antihistamine).
 
Acetaminophen 500-1000 mg P.O. (or equivalent dose of antipyretic).

Grades 3 or 4 Grade 3: Prolonged (i.e., not rapidly responsive to symptomatic medication and/or brief interruption of infusion); recurrence of symptoms following initial improvement; hospitalization indicated for other clinical sequelae (e.g., renal impairment, pulmonary infiltrates) Grade 4: Life-threatening; pressor or ventilator support indicated	
Stop Infusion.
 
Additional appropriate medical therapy may include but is not limited to:
 
 IV fluids Antihistamines NSAIDS Acetaminophen Narcotics Oxygen Pressors Corticosteroids Epinephrine 
Increase monitoring of vital signs as medically indicated until the subject
	No subsequent dosing

NCI CTCAE Grade	Treatment	Premedication at subsequent dosing
	
is deemed medically stable in the opinion of the investigator. Hospitalization may be indicated. Subject is permanently discontinued from further trial treatment administration.
 
Appropriate resuscitation equipment should be available in the room and a physician readily available during the period of drug administration.
	

9.0 Ancillary Treatment/Supportive Care

9.1 Supportive Care Guidelines

Subjects should receive appropriate supportive care measures as deemed necessary by the treating investigator. Suggested supportive care measures for the management of adverse events with potential immunologic etiology are outlined below and in greater detail in section 8.0. Where appropriate, these guidelines include the use of oral or intravenous treatment with corticosteroids as well as additional anti-inflammatory agents if symptoms do not improve with administration of corticosteroids. Note that several courses of steroid tapering may be necessary as symptoms may worsen when the steroid dose is decreased. For each disorder, attempts should be made to rule out other causes such as metastatic disease or bacterial or viral infection, which might require additional supportive care. The treatment guidelines are intended to be applied when the investigator determines the events to be related to pembrolizumab.

All blood products and concomitant medications such as antidiarrheals, analgesics, and/or antiemetics received from the first day of study treatment administration until 30 days after the final dose will be recorded in the medical records.

Note: if after the evaluation the event is determined not to be related, the site investigator is instructed to follow the reporting guidance but does not need to follow the treatment guidance. Refer to the table in section 8.1 for dose modification.

It may be necessary to perform conditional procedures such as bronchoscopy, endoscopy, or skin photography as part of evaluation of the event.

10.0 Adverse Event (AE) Reporting and Monitoring

The site principal investigator is responsible for reporting any/all serious adverse events to the sponsor as described within the protocol. Refer to the adverse event and serious adverse event sections of the protocol for detailed information..

The sponsor/sponsor-investigator is responsible for notifying FDA and all participating investigators in a written safety report of any of the following:

- Any suspected adverse reaction that is both serious and unexpected.
- Any findings from laboratory animal or *in vitro* testing that suggest a significant risk for human subjects, including reports of mutagenicity, teratogenicity, or carcinogenicity.

- Any findings from epidemiological studies, pooled analysis of multiple studies, or clinical studies, whether or not conducted under an IND and whether or not conducted by the sponsor, that suggest a significant risk in humans exposed to the drug.
- Any clinically important increase in the rate of a serious suspected adverse reaction over the rate stated in the protocol or Investigator's Brochure (IB).

Definitions

Adverse Event

Any untoward medical occurrence associated with the use of a drug in humans, whether or not considered drug related.

Suspected Adverse Reaction

Any adverse event for which there is a reasonable possibility that the drug caused the adverse event.

Expedited Reporting

Events reported to sponsor within 24 hours, 5 days or 10 days of study team becoming aware of the event.

Routine Reporting

Events reported to sponsor via case report forms

Events of Interest

Events that would not typically be considered to meet the criteria for expedited reporting, but that for a specific protocol are being reported via expedited means in order to facilitate the review of safety data (may be requested by the FDA or the sponsor).

10.1 Adverse Event Characteristics

CTCAE term (AE description) and grade: The descriptions and grading scales found in the revised NCI Common Terminology Criteria for Adverse Events (CTCAE) version 4.03 will be utilized for AE reporting. All appropriate treatment areas should have access to a copy of the CTCAE version 4.03. A copy of the CTCAE version 4.03 can be downloaded from the CTEP website. (

- a. Adverse event monitoring and reporting is a routine part of every clinical trial.
- b. Identify the grade and severity of the event using the CTCAE version 4.03.
- c. Determine whether the event is expected or unexpected (see Section 10.2).
- d. Determine if the adverse event is related to the study intervention (agent, treatment or procedure) (see Section 10.3).
- e. Determine whether the event must be reported as an expedited report. If yes, determine the timeframe/mechanism (see Section 10.4).
- f. Determine if other reporting is required (see Section 10.5).
- g. Note: All AEs reported via expedited mechanisms must also be reported via the routine data reporting mechanisms defined by the protocol (see Sections 10.6 and 18.0).

Each CTCAE term in the current version is a unique representation of a specific event used for medical documentation and scientific analysis and is a single MedDRA Lowest Level Term (LLT).

NOTE: A severe AE, as defined by the above grading scale, is NOT the same as serious AE which is defined in the table in Section 10.4.

10.2 Expected vs. Unexpected Events

Expected events - are those described within the Section 15.0 of the protocol, the study specific consent form, package insert (if applicable), and/or the investigator brochure, (if an investigator brochure is not required, otherwise described in the general investigational plan).

Unexpected adverse events or suspected adverse reactions are those not listed in Section 15.0 of the protocol, the study specific consent form, package insert (if applicable), or in the investigator brochure (or are not listed at the specificity or severity that has been observed); if an investigator brochure is not required or available, is not consistent with the risk information described in the general investigational plan.

Unexpected also refers to adverse events or suspected adverse reactions that are mentioned in the investigator brochure as occurring with a class of drugs but have not been observed with the drug under investigation.

10.3 Assessment of Attribution

When assessing whether an adverse event is related to a medical treatment or procedure, the following attribution categories are utilized:

- Definite - The adverse event is *clearly related* to the agent(s).
- Probable - The adverse event is *likely related* to the agent(s).
- Possible - The adverse event *may be related* to the agent(s).
- Unlikely - The adverse event is *doubtfully related* to the agent(s).
- Unrelated - The adverse event is *clearly NOT related* to the agent(s).

Events determined to be possibly, probably or definitely attributed to a medical treatment suggest there is evidence to indicate a causal relationship between the drug and the adverse event.

10.31 **EXPECTED Serious Adverse Events: Protocol Specific Exceptions to Expedited Reporting**

For this protocol only, the following Adverse Events/Grades are expected to occur within this population and do not require Expedited Reporting. These events must still be reported via Routine Reporting (see Section 10.5). *

System Organ Class (SOC)	Adverse event/ Symptoms	CTCAE Grade at which the event will not require expedited reporting.
Endocrine disorders	Hypothyroidism	1,2,3
	Other, specify:	1,2,3
Gastrointestinal disorders	Enterocolitis	1, 2
	Intra-abdominal hemorrhage	1,2
Respiratory, thoracic and mediastinal disorders	Other, specify:	1,2
	Pneumonitis	1,2
	Dyspnea	1,2
	Cough	1,2
	Respiratory failure	1,2
	Other, specify	1,2
Renal and urinary disorders	Nephritis	1, 2
	Hematuria	1,2
	Proteinuria	1,2
Investigations	Increased AST/ALT	1,2,3
	Increased bilirubin	1,2,3
	Creatinine increased	1,2
Infections and infestations	Hepatitis viral	1,2,3

These exceptions only apply if the adverse event does not result in hospitalization. If the adverse event results in hospitalization, then the standard expedited adverse events reporting requirements must be followed.

The following hospitalizations are not considered to be SAEs because there is no “adverse event” (i.e., there is no untoward medical occurrence) associated with the hospitalization:

- Hospitalizations for respite care
- Planned hospitalizations required by the protocol or to administer protocol directed treatment (i.e. 131I therapy)
- Hospitalization planned before informed consent (where the condition requiring hospitalization has not changed post study drug administration)
- Hospitalization for administration of study drug or insertion of access for administration of study drug
- Hospitalization for routine maintenance of a device (e.g., battery replacement) that was in place before study entry

- * Report any clinically important increase in the **rate** of a serious suspected adverse reaction (at your study) site over that which is listed in the protocol or investigator brochure as an expedited event.
- * Report an expected event that is greater in severity or specificity than expected as an expedited event
- * An investigational agent/intervention might exacerbate the expected AEs associated with a commercial agent. Therefore, if an expected AE (for the commercial agent) occurs with a higher degree of severity or specificity, expedited reporting is required.

A list of known/expected AEs is reported in the investigator brochure, package insert or the literature, including AEs resulting from a drug overdose.

10.331 Death

- Any death occurring within 30 days of the last dose, regardless of attribution to an agent/intervention under an IND/IDE requires expedited reporting within 24-hours.
- Any death occurring greater than 30 days with an attribution of possible, probable, or definite to an agent/intervention under an IND/IDE requires expedited reporting within 24-hours.
- **Reportable categories of Death**
 - Death attributable to a CTCAE term.
 - Death Neonatal: A disorder characterized by cessation of life during the first 28 days of life.
 - Death NOS: A cessation of life that cannot be attributed to a CTCAE term associated with Grade 5.
 - Sudden death NOS: A sudden (defined as instant or within one hour of the onset of symptoms) or an unobserved cessation of life that cannot be attributed to a CTCAE term associated with Grade 5.
 - Death due to progressive disease should be reported as **Grade 5 “Neoplasms benign, malignant and unspecified (including cysts and polyps) – Other (Progressive Disease)”** under the system organ class (SOC) of the same name. Evidence that the death was a manifestation of underlying disease (e.g., radiological changes suggesting tumor growth or progression: clinical deterioration associated with a disease process) should be submitted.

10.332 Secondary Malignancy

- A **secondary malignancy** is a cancer caused by treatment for a previous malignancy (e.g., treatment with investigational agent/intervention, radiation or chemotherapy). A secondary malignancy is not considered a metastasis of the initial neoplasm.
- All secondary malignancies that occur following treatment with an agent under an IND/IDE to be reported. Three options are available to describe the event:
 - Leukemia secondary to oncology chemotherapy (e.g., Acute Myelocytic Leukemia [AML])
 - Myelodysplastic syndrome (MDS)
 - Treatment-related secondary malignancy
- Any malignancy possibly related to cancer treatment (including AML/MDS) should also be reported via the routine reporting mechanisms outlined in each protocol.

10.333 Second Malignancy

- A second malignancy is one unrelated to the treatment of a prior malignancy (and is NOT a metastasis from the initial malignancy). Second malignancies require ONLY routine reporting.

10.334 Pregnancy

Prior to obtaining private information about a pregnant woman and her infant, the investigator must obtain consent from the pregnant woman and the newborn infant's parent or legal guardian before any data collection can occur. A consent form will need to be submitted to the IRB for these subjects if a pregnancy occurs. If informed consent is not obtained, no information may be collected.

In cases of fetal death, miscarriage or abortion the mother is the patient. In cases where the child/fetus experiences a serious adverse event other than fetal death, the child/fetus is the patient.

NOTE: When submitting ACCRU Adverse Event Report reports for "Pregnancy", "Pregnancy loss", or "Neonatal loss", the potential risk of exposure of the fetus to the investigational agent(s) or chemotherapy agent(s) should be documented in the "Description of Event" section. Include any available medical documentation.

10.335 Study drug overdose \geq 1000mg is the accidental or intentional use of the drug in the amount higher than the starting dose being studied.

10.3351 Any study drug overdose during the study should be noted on the CRF (AE Log found in the Forms Packet).

10.3352 All AEs associated with an overdose should both be entered on the Adverse Event CRF and reported using the procedures

detailed in Reporting of SAEs, even if the events do not meet serious criteria. If the AE associated with an overdose does not meet serious criteria, it must still be reported using the SAE form and in an expedited manner but should be noted as non-serious on the SAE form and the Adverse Event CRF.

10.4 Expedited Adverse Event Reporting Requirements for IND Agents

10.41 Phase 1 and Early Phase 2 Studies: Expedited Reporting via the **ACCRU Adverse Event Expedited Report Form** for Adverse Events That Occur Within 30 Days¹ of the Last Dose of the Investigational Agent

FDA REPORTING REQUIREMENTS FOR SERIOUS ADVERSE EVENTS (21 CFR Part 312)

NOTE: Investigators **MUST** immediately report to the sponsor **ANY** Serious Adverse Events, whether or not they are considered related to the investigational agent(s)/intervention (21 CFR 312.64)

An adverse event is considered serious if it results in **ANY** of the following outcomes:

- 1) Death
- 2) A life-threatening adverse event
- 3) An adverse event that results in inpatient hospitalization or prolongation of existing hospitalization for ≥ 24 hours
- 4) A persistent or significant incapacity or substantial disruption of the ability to conduct normal life functions
- 5) A congenital anomaly/birth defect.
- 6) Important Medical Events (IME) that may not result in death, be life threatening, or require hospitalization may be considered serious when, based upon medical judgment, they may jeopardize the patient or subject and may require medical or surgical intervention to prevent one of the outcomes listed in this definition. (FDA, 21 CFR 312.32; ICH E2A and ICH E6).

ALL SERIOUS adverse events that meet the above criteria **MUST** be immediately reported to the sponsor within the timeframes detailed in the table below.

Hospitalization	Grade 1 and Grade 2 Timeframes	Grade 3-5 Timeframes
Resulting in Hospitalization ≥ 24 hrs	7 Calendar Days	24-Hour / 3 Calendar Days
Not resulting in Hospitalization ≥ 24 hrs	Not required	

Expedited AE reporting timelines are defined as:

- "24-Hour / 3 Calendar Days" - The AE must initially be reported within 24 hours of learning of the AE, followed by a complete expedited report within 3 calendar days of the initial 24-hour report.
- "7 Calendar Days" - A complete expedited report on the AE must be submitted within 7 calendar days of learning of the AE.

¹Serious adverse events that occur more than 30 days after the last administration of investigational agent/intervention and have an attribution of possible, probable, or definite require reporting as follows:

Expedited 24-hour notification followed by complete report within 3 calendar days for:

- All Grade 3, 4, and Grade 5 AEs

Expedited 7 calendar day reports for:

- Grade 2 AEs resulting in hospitalization or prolongation of hospitalization

² For studies using PET or SPECT IND agents, the AE reporting period is limited to 10 radioactive half-lives, rounded UP to the nearest whole day, after the agent/intervention was last administered. Footnote "1" above applies after this reporting period.

Special Instructions:

- Follow site-specific reporting guidelines.
- Submit the ACCRU Adverse Event Expedited Report Form to the ACCRU SAE Coordinator via fax [REDACTED] or email [REDACTED]. The ACCRU SAE Coordinator will provide copies to Merck Global Safety by fax ([REDACTED] [REDACTED]) within 2 working days of SAE occurring or being noted.
- Other relevant safety information, drug overdoses, and Non-Serious Events of Clinical Interest should be handled in the same manner as SAEs. A copy of all 15 Day Reports and Annual Progress Reports is submitted as required by FDA, European Union (EU), Pharmaceutical and Medical Devices Agency (PMDA), or other local regulators. Investigators will cross-reference this submission according to local regulations to the Merck Investigational Compound Number (IND, CSA, etc.) at the time of submission. Additionally, investigators will submit a copy of these reports to Merck & Co., Inc. (Attn: Worldwide Product Safety; FAX [REDACTED]) at the time of submission to the FDA.
- The ACCRU SAE Coordinator will forward to [REDACTED] as appropriate. The ACCRU IND Coordinator will assist the sponsor-investigator in notifying the FDA if required.

10.5 Other Required Reporting

10.51 Unanticipated Problems Involving Risks to Subjects or Others (UPIRTSOS) in general, include any incident, experience, or outcome that meets **all** of the following criteria:

1. Unexpected (in terms of nature, severity, or frequency) given (a) the research procedures that are described in the protocol-related documents, such as the IRB-approved research protocol and informed consent document; and (b) the characteristics of the subject population being studied;
2. Related or possibly related to participation in the research (in this guidance document, possibly related means there is a reasonable possibility that the incident, experience, or outcome may have been caused by the procedures involved in the research); and
3. Suggests that the research places subjects or others at a greater risk of harm (including physical, psychological, economic, or social harm) than was previously known or recognized.

Some unanticipated problems involve social or economic harm instead of the physical or psychological harm associated with adverse events. In other cases, unanticipated problems place subjects or others at increased *risk* of harm, but no harm occurs.

Note: If there is no language in the protocol indicating that pregnancy is not considered an adverse experience for this trial, and if the consent form does not indicate that subjects should not get pregnant/impregnate others, then any pregnancy in a subject/patient or a male patient's partner (spontaneously

reported) which occurs during the study or within 120 days of completing the study should be reported as a UPIRTSO.

If the event meets the criteria for an UPIRTSO, submit to your IRB as required by your institutional policies.

10.52 Baseline and Adverse Events Evaluations

Pre-treatment symptoms/conditions to be graded at baseline and adverse events to be graded at each evaluation per the CTCAE v4.03 grading unless otherwise stated in the table below:

System Organ Class (SOC)	CTC Adverse Event Term (CTCAE v.4.03)	Baseline	At each evaluation
Investigations	Aspartate aminotransferase (AST) increased	X	X
	Alanine aminotransferase (ALT) increased	X	X
	Blood bilirubin increased	X	X
	Alkaline phosphatase increased	X	X
Endocrine Disorders	Hyperthyroidism	X	X
	Hypothyroidism	X	X
	Other: Specify hypophysitis	X	X

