4.0 Test Schedule

Tests and procedures	Active Monitoring Phase			
	≤28 days prior to registration	Day 1 Cycle 1	Day 1 Cycles 2 -8 and beyond (+/-3 days)	End of treatment (PD, withdrawal, or removal ⁹) (+7days)
History and exam, wt, ECOG PS	X	X ^{6,8}	X ⁶	X
Height	X			
Adverse event assessment	X	X ⁸	X	X
Concomitant medication review	X	X ⁸	X	
Hematology: CBC/ differential	X	X	X	X
Chemistry: SGOT (AST), ALT, alk phos, T. bili, creatinine, calcium,, Na, K, glucose, LDH, bicarbonate, uric acid, Mg, Phosphorus, total protein, blood urea nitrogen, albumin	X	X	X	
PT/INR and aPTT	X			
Urinalysis ³	X			
T3, FT4 and TSH	X	X	X	
Tumor measurement (should include at least a CT of the abdomen/pelvis, and appropriate imaging of any other target site lesions) ^{1, 10}	X		X ⁵	X
CEA	X		X ⁷	X
Pregnancy test	X ²			
Mandatory blood sample (see Section 14.0) ⁸	X	X	X ⁴	X
Mandatory tissue sample (see Section 17.0)	X			

1. Use same imaging throughout the study.
2. For women of childbearing potential only. Must be done ≤7 days prior to registration.
3. Urine blood, glucose, protein, specific gravity. Microscopic exam if abnormalities on urinalysis results.
4. Collected cycles 2, 3, 4, 8 (see Section 14.0). Kits are required for this collection.
5. Every 4 cycles beginning with end of cycle 4, and at end of treatment.
6. Directed physical exam only.
7. Every even-numbered cycle, beginning with cycle 2, and at end of treatment.
8. ≤24 hours prior to treatment.
9. Continued study treatment beyond initial radiographic disease progression may be allowed; see Section 13.4 for details. These

patients would continue follow-up per test schedule until confirmed progression.

10. To be submitted <60 days after registration

R Research funded (see Section 19.0). Mandatory research blood draws should be collected and submitted *after* the patient is registered onto the study, but before beginning study treatment.

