8.2 Dose Modification

Adverse events (both non-serious and serious) associated with pembrolizumab exposure may represent an immunologic etiology. These adverse events may occur shortly after the first dose or several months after the last dose of treatment. Pembrolizumab must be withheld for drug-related toxicities and severe or life-threatening AEs as per **the table below**.

Dose Modification Guidelines for Drug-Related Adverse Events. Use the NCI Common Terminology Criteria for Adverse Events (CTCAE) v. 4.03

CTCAE System/Organ/Class (SOC)	Adverse Event/Toxicity	Hold Treatment For Grade	Timing for Restarting Treatment	Discontinue Subject
Gastrointestinal disorders	Diarrhea/Colitis (8.4)	2-3	Toxicity resolves to Grade 0-1.	Toxicity does not resolve within 12 weeks of last dose or inability to reduce corticosteroid to 10 mg or less of prednisone or equivalent per day within 12 weeks.
		4	Permanently discontinue	Permanently discontinue
Investigations	Increased AST ALT, or Bilirubin	2	Toxicity resolves to Grade 0-1	Toxicity does not resolve within 12 weeks of last dose.
		3-4	Permanently discontinue (see exception below) ¹	Permanently discontinue
Metabolism and nutrition disorders	Hyperglycemia (8.5)	2-3	Toxicity resolves to Grade 0-1	Toxicity does not resolve within 12 weeks of last dose or inability to reduce corticosteroid to 10 mg or less of prednisone or equivalent per day within 12 weeks.
		4	Permanently discontinue	Permanently discontinue
Endocrine disorders	Hyperthyroidism/ Hypothyroidism (8.7)	3	Toxicity resolves to Grade 0-1	Toxicity does not resolve within 12 weeks of last dose or inability to reduce corticosteroid to 10 mg or less of prednisone or equivalent per day within 12 weeks.
		4	Permanently discontinue	Permanently discontinue
	Other: Hypophysitis (8.6)	2	Withhold	Administer corticosteroids and initiate hormonal replacements as clinically indicated Monitor for signs and symptoms of hypophysitis (including hypopituitarism and adrenal insufficiency)
		3-4	Withhold or permanently discontinue	
General disorders and administration site conditions	Infusion Reaction (8.9)	3-4	Permanently discontinue	Permanently discontinue

CTCAE System/Organ/Class (SOC)	Adverse Event/Toxicity	Hold Treatment For Grade	Timing for Restarting Treatment	Discontinue Subject
Respiratory, thoracic and mediastinal disorders	Pneumonitis (8.3)	2-4	Permanently discontinue	Permanently discontinue

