16.6 Secondary endpoints

These endpoints include progression-free survival (PFS), overall survival (OS), and adverse events.

- Progression-free survival (PFS) is defined as the time from study entry to the first of either disease progression or death from any cause, where disease progression will be determined based on RECIST 1.1 criteria. PFS will be estimated using the Kaplan-Meier method.
- Overall survival (OS) is defined as the time from study entry to death from any cause. OS will be estimated using the Kaplan-Meier method.
- Adverse events: The maximum grade for each type of adverse event will be summarized using CTCAE version 4.03. The frequency and percentage of grade 3+ adverse events will be summarized.

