18.1 Submission Timetables

Initial Material(s) -

CRF	Active-Monitoring Phase (Compliance with Test Schedule Section 4.0)
On-Study	
Adverse Event Baseline	
Research Blood Submission - Baseline (see Section 14.0)	
Research Tissue Submission - Baseline (see Section 17.0)	≤2 weeks after registration
Concomitant Medication - Baseline	
Path Reporting (see Section 17.0) ¹	
RECIST Measurement – Baseline	
End of Active Treatment/Cancel Notification	Submit ≤2 weeks after registration if withdrawal/refusal occurs prior to beginning protocol therapy

1. Attach a copy of OP and path reports in RAVE using the Supporting Documentation Form for documentation of disease. This is in addition to the pathology material requirements for tissue submission (Section 17.0)

Test Schedule Material(s)

CRF	Active-Monitoring Phase (Compliance with Test Schedule Section 4.0)	
	At each evaluation during treatment	At end of treatment
Evaluation/Treatment	X ²	X
Adverse Event Form	X	X
RECIST Measurement	X ¹	X ¹
Research Blood Submission	X (see Section 14.0)	
Pathology Submission		
Concomitant Medication	X	X
End of Active Treatment/Cancel Notification Form		X
Deviation Form ³	X	
ADR/AER	At each occurrence (see Section 10.0)	

1. Attach a copy in RAVE for documentation of response or progression on the Supporting Documentation Form.
2. Complete at each evaluation during Active Treatment (see Section 4.0).
3. Submit only if applicable.

Follow-up Materia(s)

CRF	Event Monitoring Phase ¹				
	q. 3 months until PD	At PD	After PD q. 6 mos.	Death	New Primary
Event Monitoring Form	X ²	X ²	X	X	At each occurrence

1. If a patient is still alive 5 years after registration, no further follow-up is required.
2. Attach a copy in RAVE for documentation of progression on the Supporting Documentation Form.

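### Liver and thyroid terms are due for grading at end of treatment, but no chemistry or thyroid test is scheduled there, so such toxicity is not systematically ascertained in patients who leave before another Day 1 draw

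*Combined protocol and SAP*

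**What the plan says.** Section 10.52 requires "adverse events to be graded at each evaluation per the CTCAE v4.03 grading unless otherwise stated in the table below". Its table has two timing columns, baseline and each evaluation. Seven terms are marked in both: AST, ALT, bilirubin, alkaline phosphatase, hyperthyroidism, hypothyroidism and hypophysitis. No exception is made for any visit.

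The test schedule in 4.0 has four columns, the last headed "End of treatment (PD, withdrawal, or removal" and so on. The row "Adverse event assessment" is marked in all four, and so is "Hematology: CBC/ differential". CEA and the mandatory research blood are also marked at end of treatment. The row that begins "Chemistry: SGOT (AST), ALT, alk phos, T. bili, creatinine" and the T3/FT4/TSH row are marked at baseline, cycle 1 Day 1 and later Day 1 visits only.

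Section 18.1 has one column headed "At each evaluation during treatment" and another for end of treatment. The Adverse Event Form is marked in both.

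On late toxicity, 8.2 says of events associated with pembrolizumab: "These adverse events may occur shortly after the first dose or several months after the last dose of treatment". The endpoint in 16.6 reads "The maximum grade for each type of adverse event will be summarized using CTCAE version 4.03", followed by the frequency and percentage of grade 3 or higher events. No time window is given.

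**The concern.** The four liver terms are graded from a laboratory value and cannot be graded without one. The two thyroid terms can be graded from symptoms, but silent disease is found only by a test. A site that follows 4.0 exactly therefore reaches the end-of-treatment visit with grading due and nothing to grade from.

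At stake is the completeness of the safety endpoint. Adverse events are a secondary objective (2.22), reported as maximum grade by type. If the period after the last dose goes untested in some patients, silent liver and thyroid events there are not counted, and the bias runs one way, towards fewer events. The empty chemistry cell also covers creatinine and glucose, although the table in 8.2 provides for renal and hyperglycemic toxicity. Grade 4 non-hematologic events that are at least possibly related also feed the accrual-suspension rule in 16.9a.

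**Working it through.** The plan states no figure on this point, so the check is a reading of the tables plus simple counting.

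**Step 1: schedule against grading requirement**

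| Row in 4.0 | Baseline | Cycle 1 Day 1 | Later Day 1 | End of treatment |
|---|---|---|---|---|
| Adverse-event assessment | X | X | X | X |
| CBC | X | X | X | X |
| Chemistry | X | X | X | none |
| T3, FT4, TSH | X | X | X | none |

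Neighbouring rows keep their end-of-treatment mark in the same extracted table, so a reading error from the PDF is unlikely. No other section schedules these tests at or after end of treatment. Event monitoring (13.5, 18.1) consists of periodic assessment and a form. Six of the seven terms in 10.52 depend on the two unmarked rows: four for the grade itself and two for detection. Hypophysitis has no row of its own in 4.0 and is not counted.

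**Step 2: which dosing intervals have a later scheduled draw**

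Under 7.4 the dose follows that day's procedures, so a Day 1 value reflects earlier doses only. For a patient who receives k doses:
- Scheduled draws that follow at least one dose, if no further Day 1 visit is attended: k − 1.
- The same, if Day 1 of cycle k + 1 is attended and the patient is then taken off treatment: k.
- Share of dosing intervals with no closing draw: 1/k in the first case, 0 in the second.

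For k = 1 without a cycle 2 Day 1 visit, there are 1 − 1 = 0 scheduled post-dose values. For k = 4 (first scan at the end of cycle 4) without a cycle 5 Day 1 visit, 1/4 = 25% of intervals are open. If that visit is attended, none are.

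**Step 3: is the open period one of continuing exposure?**

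Section 15.15 gives a half-life of 22 days at steady state. Assuming simple exponential decline, the fraction of drug remaining is 2^(−days/22):
- day 21 after the last dose: 2^(−21/22) = 0.52
- day 30 after the last dose: 2^(−30/22) = 0.39

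This is a rough guide, since a patient with few doses is not at steady state. It agrees with the protocol's own expectation in 8.2 of events after the last dose.

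**Step 4: size**

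The documents give neither the rate of liver or thyroid events after the last scheduled draw nor the share of patients who leave without another Day 1 visit. Purely by assumption, if a fraction q of 41 patients had a new event of this kind after their last scheduled draw, the number whose events would be counted only through unscheduled testing or reporting is 41q:
- q = 2%: 0.8 patients
- q = 5%: 2.1 patients
- q = 10%: 4.1 patients

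These patients are exposed to the gap; they are not all missed. Each event that is missed lowers a reported percentage by 1/41 = 2.4 percentage points if 41 patients are in the denominator.

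**The case against.** A reader might infer that the final dosing interval goes unobserved in every patient, including those stopped for toxicity. The documents do not support that. Section 7.2 requires return at least every 21 days (± 3) during treatment. A patient who attends the next Day 1, has that day's tests and is then taken off treatment has chemistry and thyroid values after the last dose. Stopping for raised AST, ALT or bilirubin itself needs a measured value, and 8.8 asks for more frequent liver tests after a grade 2 event until values return to baseline. Nor is 1/k the share of toxicity lost; it is a share of intervals, and only for patients without a further Day 1 draw.

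Other routes narrow the gap. Section 8.7 provides for thyroid tests as clinically indicated, and 15.194 asks for close monitoring of liver tests. Grade 3 and 4 events are collected regardless of attribution (10.53). Late events (10.54) and serious events (10.41) remain reportable. CBC is scheduled at end of treatment, so laboratory toxicity in general is not lost. The endpoint is secondary and descriptive, and the primary endpoint and its decision rule are untouched.

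It could also be said that end of treatment is not an evaluation in the sense of 10.52, because 18.1 gives it a separate column. This is weak: the adverse-event assessment and form are due at that visit, and the table in 10.52 offers no third timing category that would exempt it.

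The limits on scope stand. They do not remove the mismatch, because reporting routes and prompted tests depend on symptoms or on an abnormality already known. Silent changes in transaminases or TSH are what they leave out.

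**Conclusion.** The inconsistency is certain: 10.52, read with 4.0 and 18.1, requires grading at end of treatment for which 4.0 schedules no test. The consequence is narrower. In patients who leave treatment before another Day 1 draw, liver, other chemistry and thyroid toxicity after the last dose is not systematically ascertained. The likely effect is some under-counting of asymptomatic events in the 16.6 summaries. An effect on the 16.9a rule is possible but would matter only if the count were near its boundary of 4 of the first 10 treated patients, or 40% thereafter.

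The number of patients or events cannot be derived from the documents; the figures for assumed rates of 2% to 10% are illustrations. The conclusion rests on the end-of-treatment cells being empty in the source table, as the neighbouring rows indicate. It is worth correcting because the remedy is small, not because the loss is shown to be large.

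**What to change.** Reconcile 4.0 with 10.52 and 18.1 by marking the chemistry panel and T3/FT4/TSH under end of treatment. Blood is already drawn at that visit for CBC, CEA and research samples, so the cost is one extra chemistry panel and one extra thyroid panel per patient, at most 41 of each. Sample size, primary endpoint and treatment rules do not change.

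For patients already past that visit, and for all patients if the schedule is left as it is, state in 10.52 that laboratory terms are graded at end of treatment only where measured. Report beside the 16.6 summaries how many patients had a liver and a thyroid value after their last dose. This costs a sentence and a count; it makes the gap visible but does not close it.
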